1. INTRODUCTION

1.1 Disease Background

Oropharynx cancer (OPC), a subset of squamous cell carcinoma of the head and neck (SCCHN), is often associated with human papillomavirus (HPV) infection. It has been proposed that the favorable prognosis observed in HPV+ vs. HPV- OPC may be due to immune responses directed against viral antigens. Tumor-infiltrating CD4+ and CD8+ T cells in OPC are associated with a favorable prognosis. HPV-specific T cells can also be grown from tumor biopsies, suggesting that at least some of the infiltrating T cells are HPV-specific. Immune responses to several tumor-associated determinants have also been implicated in HPV+ and HPV-HNSCC, including p53, Mage-A3, Her2/neu, and survivin.

Immune responses directed against tumors are one of the body's natural defenses against the growth and proliferation of cancer cells. However, over time and under pressure from immune attack, cancers develop strategies to evade immune-mediated killing allowing them to develop unchecked. One such mechanism involves upregulation of surface proteins that deliver inhibitory signals to cytotoxic T cells. Programmed cell death ligand 1 (PD-L1) is one such protein, and is upregulated in a broad range of cancers with a high frequency, with up to 88% expression in some tumor types. In a number of these cancers, including lung (Mu et al, 2011), renal (Thompson et al, 2005; Thompson et al, 2006; Krambeck et al, 2007), pancreatic (Nomi et al, 2007; Loos et al, 2008; Wang et al, 2010), ovarian cancer (Hamanishi et al, 2007), and hematologic malignancies (Andorsky et al, 2011; Brusa et al, 2013) tumor cell expression of PD-L1 is associated with reduced survival and an unfavorable prognosis.

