1.3 Research hypothesis

Based on preliminary data showing that the presence of HPV antigens is contributing to increased anti-tumor T cell activity in patients with SCCHN, we hypothesize that immunotherapy with PD-L1 antibody will lead to more intense and efficient specific immune activation against the SCCHN tumor in HPV + patients compared with HPV - patients. We also hypothesize that an extensive analysis of the blood and saliva might lead to identification of markers predictive of a more efficient response to PD-L1 inhibition. Lastly we would like to test the ability of PET scan to detect an increased immune response. One can hypothesize that a corresponding increase in the immune response with an increase in the number of infiltrative activated immune cells could be associated with an increase in metabolic activity measured by PET SUV. Similarly, an effective anti-tumor activity of the

activated immune response could lead to decreased metabolic activity. We are interested in evaluating the dynamic in the metabolic activity early in the treatment and to attempt to detect potential consistency that could be used in future therapeutic paradigms.

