2. STUDY OBJECTIVES

2.1 **Primary objectives**

- 2.1.1 The primary objective of this study is to investigate the effect of Durvalumab on local and systemic immune activation by HPV status in patients with oral cavity and oropharynx HNSCC. This will be done by:
 - a) Examining the effects of Durvalumab on systemic immune response to HPV and tumor associated antigens
 - b) Examining the effects of Durvalumab on immune regulatory mechanisms.
 - c) Exploring the association between levels of immune-regulatory miR in plasma and saliva and immune response.

Results will be compared between HPV positive and negative patients to identify a possible differential effect of treatment with Durvalumab. Level of local immune response in the primary tumor and in the regional lymph nodes will be compared whenever possible.

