8.3.1 Immunogenicity sampling and evaluation methods

Blood and saliva will be collected pre- and post-treatment with Durvalumab.

Blood (20 ml) will be drawn into EDTA tubes. Samples will be labelled and transported at rrom temperature within one hour to [name] laboratory in Hanes building 5th floor. Peripheral blood mononuclear cells (PBMC) are isolated from whole blood by density gradient centrifugation using Lymphocyte Separation Medium (Mediatech) and Leucosep tubes (Greiner Bio-one). Whole blood is centrifuged at 410 × g for 10 minutes and the plasma layer is collected, centrifuged for 10 minutes at 885 × g, and the supernatant frozen at -80° C for subsequent experiments. The whole blood is diluted 1:1 with RPMI (Mediatech) and the PMBCs isolated per manufacturer's guidelines. Cells at the interface are harvested and washed once with RPMI, and red blood cells are lysed with ammonium chloride lysis buffer. Cells are washed, counted, and immediately used fresh for staining and flow cytometry analysis, or 10 million PBMCs are frozen per milliliter of freezing solution (10% DMSO 10% FBS-supplemented RPMI) per NUNC cryovial. PBMCs are frozen in a Nalgene Cryo 1°C freezing container per manufacturer's instructions and stored in liquid nitrogen thereafter.

PBMC and plasma will be used for the following assays:

1. Examine the effects of Durvalumab on systemic immune response to HPV and tumor associated antigens. Peripheral blood mononuclear cell interferon- γ production in vitro in response to commercially available peptide pools corresponding to HPV, p53, Mage-A3, Her2/neu, and survivin will be determined.

PBMC that have been separated by gradient centrifugation and cryopreserved are thawed at 37 °C, diluted in 5 ml RPMI, and incubated at 37 °C for 1 hour. Cells are then pelleted at 200g, resuspended in complete medium, counted with trypan blue, and suspended at 4x106/ml and plated in 100 µl in 96 well conical wells. PBMC are then cultured with 20 µg/ml of WT-1, p53, Her2/neu, Mage-A3, telomerase, and survivin peptide mixtures ProMix Peptide Pools (Proimmune Inc.). As a control PBMC are also stimulated with anti-CD3 plus anti-CD28 antibody (BD Pharmingen). After 3 days, culture supernatants are collected and assayed using commercially available ELISA kits according to the recommendation of the manufacturer. Results are expressed as a concentration.

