9.2 Immunologic response

1. Effect of Durvalumab on systemic immune response to HPV and tumor associated antigens

Blood will be collected before and after treatment (before surgery) with Durvalumab. Peripheral blood mononuclear cell interferon- γ production in vitro (ELISA) in response to commercially available peptide pools corresponding to HPV, p53, Mage-A3, Her2/neu, and survivin will be measured by commercially available ELISA kits. Responses of patients whose tumor are HPV+ will be compared to those that are HPV-.

2. Examine the effects of Durvalumab on immune regulatory mechanisms:

- Blood samples will be collected before and after treatment with Durvalumab. The following immune effector and regulatory responses will be assessed in blood using standard flow cytometric techniques:

CD4+, CD8+, CD4+FoxP3+ Treg, and CD45RO+CD4+ memory T cells; CD3-CD56+ NK cells, and CD14-HLA-DR-CD15+ MDSC. Average change in pre- and post-treatment measurements will be compared between HPV+ and HPV- patients.

- Tumor (primary tumor and regional involved lymph nodes) will be collected before treatment (tissue biopsy) and at the time of surgery, after treatment. PD-1+CD4+, PD 1+CD8+, PD-1L+, and Foxp3+CD4+ tumor-infiltrating cells will be quantified (0 to 3+) using standing immunofluorescence techniques. The results of patients whose tumor are HPV+ will be compared to those that are HPV-.

3. Explore the association between levels of immune-regulatory miR in plasma and saliva and immune response. Blood and saliva samples will be collected before and after treatment with Durvalumab. Tumor (primary tumor and regional involved lymph nodes) will be collected before treatment (mandatory biopsy) and at the time of surgery. Levels of immune-regulatory miRs will be quantified using PCR-based techniques. Levels and change in levels before and after treatment will be compared among saliva, blood and tumor tissue.

The relationship between levels of the miRs and the immune response to HPV, immune response to tumor associated antigens, and immune regulatory molecules/cells will be assessed.

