11. STATISTICAL METHODS AND SAMPLE SIZE DETERMINATION

11.1 Description of analysis sets

Primary Objectives

The primary objectives of this pilot study are to investigate the effect of Durvalumab on local and systemic immune activation and compare the results in HPV positive and HPV negative patients with oral cavity and oropharynx HNSCC. Tumor tissue, blood and saliva will be collected before and after treatment with Durvalumab and will be analyzed for systemic immune response to HPV and tumor associated antigens and impact on immune regulatory mechanisms in tumor and blood. Levels of immune-regulatory miR in plasma and saliva will be correlated with other parameters of the local and systemic immune response in order to identify possible predictors of response. Results will be compared between HPV positive and negative patients to identify a possible differential effect of treatment with Durvalumab. Level of local immune response in the primary tumor and in the regional lymph nodes will be compared whenever possible.
Secondary Objectives

- A. Investigate the effect of the treatment with Durvalumab on measures of tumor volume (from the CT scan) and tumor activity (from the PET scan).
- B. Evaluate the safety of a short induction treatment with Durvalumab.

Primary Endpoints:

Since this is a pilot study and does not have a specific primary efficacy analysis, there are several primary endpoints (rather than a single primary efficacy endpoint) that will be collected. These can be described in three broad categories within the area of local and systemic immune activation. The categories are effects of Durvalumab on 1) systemic immune response to HPV and tumor associated antigens; 2) immune regulatory mechanisms; and 3) immune-regulatory miR responses as measured in plasma, saliva or tumor. Each of these categories has several endpoints that will now be described.

- 1. Systemic immune response to HPV and tumor associated antigens:
 - a. Peripheral blood mononuclear cell interferon-γ production in vitro (ELISA) in response to commercially available peptide pools corresponding to HPV, p53, Mage-A3, Her2/neu, and survivin will be determined.
- 2. Immune regulatory mechanisms.
 - a. The following immune effector and regulatory responses will be assessed in blood using standard flow cytometric techniques: CD4+, CD8+, CD4+FoxP3+ Treg, and CD45RO+CD4+ memory T cells; CD3-CD56+ NK cells, and CD14-HLA-DR-CD15+ MDSC.

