11.2.2 Efficacy Analyses

As stated above, there are several primary efficacy measures for this protocol. In addition, this is not a randomized clinical trial, thus there is not one primary efficacy analysis, rather there are a series of primary analyses proposed to be performed examining each of the primary efficacy measures described above.

Analysis of immunogenicity

- Peripheral blood mononuclear cell interferon-γ production in vitro (ELISA) in response to commercially available peptide pools corresponding to HPV, p53, Mage-A3, Her2/neu, and survivin will be compared between patients who are HPV+ and HPV- using 2 sample t-tests. These measures will be compared in several ways. First, baseline, pre-treatment levels will be examined using descriptive statistics (n, mean, standard deviations, range). These measures will be examined overall and by HPV (+/-) groups. For each measure, and time point, 95% confidence intervals will be estimated. Next, two sample t-tests will be performed to compare levels of the measures at baseline. Next, measures taken post-treatment will be examined in a similar manner (descriptive statistics and 2-sample t-tests). Finally, comparisons between HPV+ and HPV- groups will be made by comparing the changes (pre-treatment to posttreatment) between groups using 2-sample t-tests.
- 2) Concentration of certain immune effector and regulatory cells will be assessed in blood (CD4+, CD8+, CD4+FoxP3+ Treg, and CD45RO+CD4+ memory T cells; CD3-CD56+ NK cells, and CD14-HLA-DR-CD15+ MDSC) pre- and post- treatment. Descriptive statistics, confidence intervals will be calculated and 2-sample t-tests will be performed as described above for the interferon- γ analyses.
- 3) Tumor-infiltrating immune-regulator and effector cells will be quantified (0 to 3+) using standing immunofluorescence techniques. Counts and percents will be calculated for these measures overall and by HPV (+/-) groups pre- and post-treatment. Fisher exact tests will be used to compare groups at pre- and post- treatment. Stuart-Maxwell tests (generalizations of the McNemar's Test) will be used to examine changes between groups (HPV +/-) from pre- to post- treatment.

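### The only stimulation step described for primary endpoint 1a has no HPV peptide pool, although the endpoint and its analysis require one

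*Combined protocol and SAP*

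**What the plan says.** Section 2.1 gives primary objective a as "Examining the effects of Durvalumab on systemic immune response to HPV and tumor associated antigens". Section 8.3.1 opens assay 1 with the response to "commercially available peptide pools corresponding to HPV, p53, Mage-A3, Her2/neu, and survivin will be determined". The synopsis (Immune Response Assessments, item a), Section 9.2 (item 1), Section 11.1 (endpoint 1a) and Section 11.2.2 (item 1) name the same five pools; Section 9.2, for example, has "peptide pools corresponding to HPV, p53, Mage-A3, Her2/neu, and survivin will be measured by commercially available ELISA kits".

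The next paragraph of Section 8.3.1 describes the bench work: thawing, counting, plating, stimulation for 3 days, then ELISA. There the cells are cultured at 20 µg/ml with "WT-1, p53, Her2/neu, Mage-A3, telomerase, and survivin peptide mixtures ProMix Peptide Pools". The only other stimulus is anti-CD3 plus anti-CD28, as a control. The protocol describes no other stimulation.

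Section 11.2.2 plans two-sample t-tests of HPV-positive against HPV-negative patients on each pool at baseline, after treatment and on the change. Section 9.2 (item 3) and the synopsis (item d) also plan to relate microRNA levels to the immune response to HPV.

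**The concern.** The endpoint and the procedure that is meant to produce it do not match, and the missing pool is central to the study question. Section 1.3 builds its hypothesis on preliminary data that "the presence of HPV antigens is contributing to increased anti-tumor T cell activity in patients with SCCHN". A laboratory working from the culture paragraph would generate no HPV-stimulated result. It would also generate WT-1 and telomerase results that no endpoint or analysis covers.

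A reader who assumes that HPV is intended still cannot run the condition from the protocol. No section gives the HPV type, the protein or proteins, the product or the concentration, and different choices would measure different responses. The HPV PCR done at screening determines tumour status and says nothing about T-cell response.

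**Working it through.** No sample-size or power figure is involved. The check compares the lists and then counts the analyses affected.

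**Pools, side by side**

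| Antigen | Endpoint list (synopsis; 8.3.1 opening; 9.2; 11.1; 11.2.2) | Culture step (8.3.1) |
|---|---|---|
| HPV | yes | **no** |
| p53 | yes | yes |
| Mage-A3 | yes | yes |
| Her2/neu | yes | yes |
| survivin | yes | yes |
| WT-1 | no | **yes** |
| telomerase | no | **yes** |

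- In both lists: 4.
- Endpoint pools with no described stimulation: 1 of 5 (HPV).
- Cultured pools that belong to no endpoint: 2 of 6 (WT-1, telomerase).

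**Which list fits the rest of the protocol.** Section 1.1 states: "Immune responses to several tumor-associated determinants have also been implicated in HPV+ and HPV-HNSCC, including p53, Mage-A3, Her2/neu, and survivin". Those are exactly the four non-HPV endpoint pools, and neither extra antigen is among them. The same section discusses HPV-specific T cells. The background therefore supports the endpoint list.

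**Whether the culture list is only illustrative.** Section 8.3.1 introduces its flow cytometry antibodies with a word that leaves the list open. The culture sentence has no such word. It gives concentration, product and supplier and reads as a complete recipe. The sentence is intact, so text extraction does not explain the gap.

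**Analyses affected (Section 11.2.2, item 1)**

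- Between-group t-tests per pool: baseline, post-treatment, change = 3.
- Over the endpoint: 3 × 5 pools = 15.
- HPV share: 3 / 15 = 20%.
- If the six blood cell populations in item 2 are counted on the same scheme: 3 × (5 + 6) = 33, and 3 / 33 ≈ 9%, before the tumour-cell and microRNA analyses.

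The HPV descriptive statistics and confidence intervals would be lost with the tests.

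**Cells needed (Section 8.3.1: 100 µl per well at 4 million per ml)**

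- Per well: 0.1 ml × 4 million/ml = 0.4 million.
- As written: 6 pools + positive control = 7 wells; 7 × 0.4 = 2.8 million.
- Five endpoint pools + positive control = 6 wells; 6 × 0.4 = 2.4 million.
- The same plus a medium-only well = 7 wells; 2.8 million.
- The same, keeping WT-1 and telomerase as exploratory = 9 wells; 9 × 0.4 = 3.6 million.

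These counts assume single wells and one HPV pool.

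**The case against.** The strongest reply is that this is an incomplete description and not a decision to drop HPV. The culture sentence does not exclude HPV. It sits under a heading and directly after a sentence that both require it, and its present tense suggests a standard laboratory method carried over. Intent runs five statements to one. That is a plausible reading, and it is why the loss is a risk and not a certainty. It does not supply the missing condition, because nobody can tell from the protocol which HPV pool to use.

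A second reply is that the harm may be recoverable. Cells are frozen at 10 million per vial, against 2.8 million for seven single wells, so an omitted pool might be run later. This has some force, but the number of vials per draw, replicates and post-thaw recovery are not given. A pre-treatment sample cannot be redrawn after durvalumab, and Section 8.3.1 keeps leftover samples beyond the study report only with the patient's agreement.

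Third, the study is a descriptive pilot with many primary measures. The 20% applies within endpoint 1a only and falls to about 9% once the blood cell measures are counted. In the microRNA objective only the HPV response is lost; the responses to tumour-associated antigens and the regulatory cells and molecules remain. Both limits are accepted.

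**Conclusion.** The concern holds. Section 8.3.1 contradicts itself: its endpoint sentence includes HPV, and the only stimulation procedure in the protocol does not. If that procedure is followed literally, one of the five endpoint pools yields no data. The 3 HPV tests of the 15 planned for endpoint 1a cannot be run, and the HPV part of the microRNA association loses its response variable. The other four pools, the flow cytometry, the tumour markers and the sample-size statement are untouched.

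The mismatch itself is certain. The harm depends on the laboratory working from the culture paragraph and on stored cells not being available to make good the omission; the documents settle neither. The point should be corrected, since it concerns the first-named part of a primary objective and is cheap to put right.

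**What to change.** In the culture step of Section 8.3.1, list the five endpoint pools. For HPV, state the type, the protein or proteins covered, the product and the concentration. Remove WT-1 and telomerase, or keep them and label them exploratory in Sections 8.3.1 and 11.1.

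A minor, separate addition: the only control named is a positive one, and the handling of background interferon-gamma is not stated. A medium-only well per sample, with Section 11.2.2 defining the analysed value as stimulated minus unstimulated, would settle that. The main correction does not depend on it.

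The cost is protocol wording and purchase of the HPV pool. On the single-well, one-HPV-pool assumption, exchanging WT-1 and telomerase for HPV and a medium-only well leaves the layout at 7 wells and 2.8 million cells per sample. Retaining the two extra pools as well raises it to 9 wells and 3.6 million. Total cell need cannot be estimated without the replicate number, vials per draw and post-thaw recovery. Dosing, visits and the planned blood draws do not change.

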8.3.3 Estimate of volume of blood to be collected

The total volume of blood that will be drawn from each subject in this study is as follows:

Assessment		Sample volume (mL)	No. of samples	Total volume (mL)
Safety	Clinical chemistry	10	9	90
	Hematology	5	9	45
Immune Studies		20	2	40
Additional Research S	Samples	20	3	60
(with patient's consen	t per ICF)			
Total: 235 ml				

Table 6. Volume of Blood to Be Drawn From Each Subject

8.3.4 Fresh tumor biopsies

Procurement of a fresh tumor sample before treatment is mandatory for enrolling the patient in this study, unless a tumor sample has already been banked in our Tumor Tissue Bank at the time of initial diagnostic biopsy, under Wake Forest University IRB approved and monitored Protocol Number BG98-391.

A separate consent for banking tumor tissue is available for all patients undergoing biopsies and surgeries at our institution.

Due to tumor location in the study patient population (oral cavity and oropharynx) biopsies will be performed in the office. However, if needed in exceptional cases, procedure will be scheduled in OR. One tumor sample and one normal tissue sample will be collected by incisional biopsy under local anaesthesia by our co-PI investigator, [name] of ENT or his designee.

Biopsy tissue will be placed immediately in special tubes containing transporting media, readily available and [name], tissue procurement officer, will be called in advance and will transport the tissue to our Tumor Tissue Bank where the sample will be flash frozen and stored.

Additional samples of fresh primary tumor tissue and adjacent normal tissue as well as sample of tumor involved lymph node tissue (whenever the case) will be collected for the same patient from the surgical

specimen obtained at the time of surgery, after conclusion of the treatment with Durvalumab. [name] will be informed in advance about the time of surgery and she will attend the surgical specimen in the Department of Pathology, collect the specimens with the help of the Pathologist on call and transport the specimen to the Tumor Tissue Bank where it will be fresh frozen and stored.

Tissue collection will be monitored by the IRB under the current protocol, including maintenance of patient confidentiality and the HIPAA-compliant sample database. The tissue as well as blood samples are kept in the Tumor Tissue Core Laboratory of the 4th floor of the Hanes Building, which is either manned by a member of the Tumor Tissue Core Laboratory or is locked at all times. The Core Lab's database resides on the Comprehensive Cancer Center of Wake Forest University's (CCCWFU) secure server behind the WFUHS firewall with HIPAA-compliant security. The database is only accessible by the Tumor Tissue Core personnel.

Fresh frozen tissue collected before and after treatment will be used for the following assays for the following immune assessments:

Tumor (primary tumor and involved lymph node) will be assayed using standing immunofluorescence techniques for PD-1+CD4+, PD 1+CD8+, PD-1L+, and Foxp3+CD4+ tumor-infiltrating cells. The results will be quantified (0 to 3+).

Immunohistochemical staining will be carried out on 4µm-thick sections utilizing an Autostainer Plus (Dako - Agilent Technologies) with appropriate positive and negative controls. Sections are baked for 60 minutes at 60 °C in a dehydration oven and heat-induced epitope retrieved in the PT link (Dako – Agilent technologies) using EnVision FLEX target retrieval solution for 20 minutes at 97 °C then cooled to room temperature in TBST Wash buffer for 5 minutes. Slides are incubated with the diluted antibodies. Antibody detection will utilize the Envision FLEX kit (K8023) with a DAB chromagen for visualization according to the manufacturer's instructions (Dako – Agilent technologies). Slides are then counterstained with hematoxylin. The percentage of tumor which have an infiltrate of lymphocytes or macrophages will be estimated and the average number of positive immune cells per high power field (HPF) in a minimum of 4 representative HPF areas will be determined utilizing a semi-quantitative four tiered scale used for scoring lymphocytes (0= no lymphocytes, 1= 1-10/HPF, 2= 11-50/HPF and 3= >50/HPF) and macrophages (0= no macrophages, 1= 1-50/HPF, 2= 50-100/HPF and 3=>100/HPF). Lymphocyte and macrophage infiltrate scores are obtained by multiplying these scores to attain a score from 0-300.

miRNA will be quantified in tumor tissue and involved lymph node using PCR-based techniques (as described in 8.3.1).

Remaining tissue samples will be retained for future research after the study report has been finalized if agreed by patients in the ICF. Otherwise it will be disposed.

